A medical food is a special category of supplement approval by the FDA where physicians prescribe it for nutritional treatment of specific medical conditions. The medical food to be used by patients in this study contains not only all the macular carotenoids in micelle formulation for improved absorption, but also significant cofactors, such as vitamins, minerals, ALA, astaxanthin, N-acetylcysteine, carnosine and others. All of these ingredients working together should significantly improve the mitochondrial, antioxidant and anti-inflammatory functions of the retina. This should allow creation of less damage to critical elements of the retina and less toxic waste such as oxidized cholesterol and oxidized polyunsaturated fatty acids which are the major components of the sub-RPE and Bruch's membrane deposits. This controlled study will attempt to show that using a medical food designed to optimize retinal metabolism and antioxidant capacity will exert a positive effect in subclinical macular degeneration, which is greater than supplementation with AREDS2 and will also improve measured functions into the range of function in untreated normal patients.

STUDY:

All study candidates are routine patients in a general ophthalmology practice. All patients who are interested will be offered the opportunity to participate in this controlled study of the effect of a nutritional food on subclinical macular degeneration. Each patient will undergo a screening AdaptDx to separate patients with normal dark adaptation from those with abnormal dark adaptation. All patients will receive the same exams at baseline, 3 months and 6 months. For details, see the listing below. Those who are confirmed as normal with extended dark adaptation testing will receive no treatment precisely because they are defined as not having a problem needing this treatment. Those who are confirmed with early macular degeneration by photographically visible drusen and have dark adaptation scores of less than 10 minutes will receive treatment by ingesting a commercially available medical food, containing all 3 macular pigment as well as essential cofactors and other antioxidants, or AREDS2, randomized 2:1 for 6 months. If positive effects are noted, it is possible that the study might be extended. The tasks below are part of standard diagnostic clinical eyecare practice.

- Baseline, 3 month and 6 month examinations
 - History
 - Risk factors
 - Best corrected visual acuity

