 - Best corrected contrast sensitivity (CSV 1000)
 - Intraocular pressure, nondilated slit-lamp exam
 - Dark adaptation (AdaptDX, extended exam)
 - Macular pigment optical density (MapcatSF)
 - Macular ocular coherence tomography (Zeiss Cirrus OCT)
 - Fundus photography (Zeiss VisuCam Pro)

Because these patients will have additional problems found in routine clinical practice, other exams may occur for other problems and will not be considered part of the study data. Should any adverse effects be noted thought to be from the study treatment, the patient will be examined to understand the effect and if it is felt to be not significant, the patient will be asked to continue in the study. In the highly unlikely event a serious adverse effect is noted the patient will be terminated from the study and appropriate treatment will be undertaken.

DATA COLLECTION:

The data will be maintained on standardized forms and printable graphics, as well as in the patient's routine clinical file. To protect identifiable information, files will be locked in a file cabinet, accessible only the PI and the study coordinator. Data will be transcribed without

personally identifiable information into standard Excel files and analyzed as appropriate using standard statistical techniques.

STUDY REQUIREMENTS:

This study will be conducted with the protocol, good clinical practices and applicable regulatory requirements. This is a no significant risk study, using commercially available supplements, Lumega-Z or AREDS2, containing 2 or 3 of the three carotenoids that are FDA “generally recognized as safe” for food supplementation and are found in all healthy retinas. All examinations are noninvasive and are performed with FDA cleared, commercially available medical devices in routine clinical use.

The study population consists of 90 male and female patients in a routine clinical practice age 60 and over who have early macular degeneration as defined as a few drusen visible on Visucam and have an AdaptDx score less than or equal to 10 minutes. No vulnerable populations will be studied.

The patient will be studied for improvements in ocular function. Primary endpoints would be improvement in macular pigment optical density long form, improvement in best corrected contrast sensitivity and improvement in best corrected vision. Secondary endpoints would be improvement of AdaptDx long form time or a reduction in drusen.

The study supplements for each

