At the end of the trial period, data will be collected by the Principal Investigator and analyzed by professional optical engineers at Western University of Health Sciences, Pomona CA. The data provided will only contain patient ID, age, and sex, without containing any identifying details about each participant. Data will be analyzed upon measurement quality, according to the respective manufacturer procedures, in each outcome measure. In the event which data is missing or incomplete, we will evaluate the appropriate measures to include the available information and consult with qualified professionals.

Preliminary and sub-analyses will be performed using the statistical programming software, SPSS Systems. The objective is to examine the distribution and potential relationships within data sets through standardized descriptive-numerical summaries. Statistical analysis strategies may include a mixed-design Analysis Of Variance (ANOVA) to examine the following outcome measures across the three time-points of data collection; including visual acuity, contrast sensitivity, dark adaptation recovery, and MPOD levels. A post hoc sub-analysis of paired sample t-test may be used (either Bonferroni correction or Tukey test) to evaluate the change in each outcome measure parameter, if needed, in respect to each treatment group. Additionally, each group-measurement may be separated and analyzed by eye; to evaluate inter-eye differences from each treatment. Results of the statistical analysis will be analyzed as group averages of each outcome measurement.

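### The only model named for the three visits excludes incomplete patients by default, and the plan names no method that would use their data

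*Combined protocol and SAP*

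**What the plan says.** The STUDY section sets three examinations: "All patients will receive the same exams at baseline, 3 months and 6 months". The unheaded statistical analysis text at the end of the combined document names one model for them, as something the strategies may include: a "mixed-design Analysis Of Variance (ANOVA) to examine the following outcome measures across the three time-points of data collection". The outcomes listed are visual acuity, contrast sensitivity, dark adaptation and MPOD. The only other test is within-group and optional: "A post hoc sub-analysis of paired sample t-test may be used".

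On missing data, the same text says: "In the event which data is missing or incomplete, we will evaluate the appropriate measures to include the available information and consult with qualified professionals". On software: "Preliminary and sub-analyses will be performed using the statistical programming software, SPSS Systems". It does not name an SPSS procedure. The DATA COLLECTION section refers only to standard statistical techniques. The available text contains no imputation rule, likelihood-based model or definition of an analysis set.

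The STUDY section also provides that after a serious adverse effect, described there as highly unlikely, "the patient will be terminated from the study". It does not say how data already collected from such a patient are analysed.

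**The concern.** A classical mixed-design ANOVA (SPSS repeated-measures GLM) takes one row per patient with all three visits filled. A patient who leaves after month 3 contributes nothing to that outcome's analysis, although baseline and 3-month values exist. A patient who misses only month 3 loses a valid 6-month value. The default behaviour of the one named model therefore works against the plan's own aim of keeping incomplete data in.

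Two things are at stake. The comparison of Lumega-Z with AREDS2 can become one of patients who attended every visit. If leaving is related to the 3-month result in one arm, completers flatter that arm. Observed 6-month values can also be discarded, in a study of 90 patients with no stated power calculation to absorb the loss. Because no method is fixed, the choice may be made once the pattern of missing data is visible.

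**Working it through.** The documents state no dropout rate, SD, effect size or power, so there is no figure of the plan's own to reproduce. Everything below is illustrative.

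**Inputs from the documents.** Three visits (STUDY); 90 patients (STUDY REQUIREMENTS); 2:1 randomisation (PURPOSE and STUDY). The 60:30 split assumes that all 90 are randomised.

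**1. Patients kept.** Assume each follow-up visit is missed independently with probability m. Complete cases are (1−m)², and patients with a 6-month value are 1−m.

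| m | complete | of 90 | 6-month value | of 90 |
|---|---|---|---|---|
| 5% | 90% | 81.2 | 95% | 85.5 |
| 10% | 81% | 72.9 | 90% | 81.0 |
| 15% | 72% | 65.0 | 85% | 76.5 |

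With the standard error proportional to 1/√n, dropping the 6-month values of patients who missed month 3 inflates it by 1/√(1−m) = 1.026, 1.054 or 1.085. If missingness is pure dropout, no 6-month value is lost in this way.

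**2. Bias from selective dropout.** Assume no true effect, SD 1 at each visit and a common correlation ρ between visits (compound symmetry). In one arm, a fraction p of those below the median 3-month change drop out after month 3, against 10% of the rest of that arm. Dropout in the other arm is at random.

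- The 3-month change has SD √(2(1−ρ)).
- Its covariance with the 6-month change is 1−ρ, so the regression slope of 6-month on 3-month change is (1−ρ)/(2(1−ρ)) = 0.5.
- The mean standardised 3-month change among completers is √(2/π) × (0.9 − (1−p))/(0.9 + (1−p)), with √(2/π) = 0.798.
- Bias in 6-month change = 0.5 × √(2(1−ρ)) × that mean.

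For p = 30% and ρ = 0.5: 0.5 × 1 × 0.798 × 0.2/1.6 = 0.050. For p = 40%: 0.5 × 1 × 0.798 × 0.3/1.5 = 0.080.

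| p | ρ = 0.5 | ρ = 0.7 | ρ = 0.8 |
|---|---|---|---|
| 30% | 0.050 | 0.039 | 0.032 |
| 40% | 0.080 | 0.062 | 0.050 |

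The bias applies to change from baseline. The covariance of the 3-month change with the raw 6-month value is ρ − ρ = 0, so the raw 6-month contrast is unbiased under this mechanism.

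**3. Scale.** With 60:30 and 20% loss (48 and 24 left), the standard error of the change contrast is √(2(1−ρ)) × √(1/48 + 1/24), which is 0.25 at ρ = 0.5 and 0.16 at ρ = 0.8. The bias is thus about 0.2–0.3 of a standard error (0.050/0.25 = 0.20; 0.080/0.25 = 0.32).

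**4. Likelihood model.** Here dropout depends only on observed baseline and 3-month values, so a likelihood analysis that includes them is approximately unbiased. A separate simulation used 4,000 trials, 60:30, ρ = 0.6, a true difference in 6-month change of 0.50 SD, dropout in the Lumega-Z arm rising smoothly as the 3-month change worsened, and about 21% dropout overall. Completers gave 0.59 and the likelihood estimate gave 0.50. The spread across trials was 0.224 and 0.222, so under pure dropout the gain is in bias and hardly at all in precision.

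**The case against.** The strongest reply is that the plan commits to none of this. Several stronger readings are tempting, and the documents do not support them.

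- A reader might infer that the plan deletes incomplete patients as a rule. It does not. The ANOVA is only something the strategies may include, no SPSS procedure is named, and neither MIXED nor prior imputation is ruled out. Deletion is the default of the classical form.
- A reader might infer that the plan promises to use partial data and then contradicts itself. Its words are "In the event which data is missing or incomplete, we will evaluate the appropriate measures to include the available information", which is an undecided intention. That the choice falls after data collection is a reasonable inference but is not stated.
- A reader might infer that an incomplete patient vanishes from every analysis. Deletion is outcome by outcome, and a paired t-test could use a baseline and 3-month pair. That test is optional and within-group, however, so it does not restore the patient to the comparison of arms.
- A reader might take the termination provision as evidence of material attrition, or the liquid form of Lumega-Z as evidence of worse persistence. The protocol presents the first as rare. On the second, the available text does not describe the AREDS2 intake, so burden cannot be compared. Differential persistence is plausible but not shown.

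The bias is also modest and rests on dropout assumed to be selective in one arm only. All of this limits the claim. What stands is that the optional wording supplies no alternative: one three-visit model is named, its usual form excludes incomplete patients, and nothing in the available text says how their data would be kept.

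**Conclusion.** The point holds in this limited form and should be acted on. The sole three-visit model named excludes incomplete patients by default, outcome by outcome, and the stated aim of including their data has no method behind it. At assumed miss rates of 5–15% per follow-up visit, 10–28% of patients would be left out, while only 5–15% lack a 6-month value. Under the assumed selective dropout, the contrast in 6-month change is biased by about 0.03–0.08 SD, or roughly 0.2–0.3 of a standard error. These sizes rest on assumed dropout rates, independence of missed visits, compound symmetry and a 60:30 split, none of which the documents give. With little missing data the effect would be small. With non-selective dropout the cost would be mainly precision.

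**What to change.** Replace the mixed-design ANOVA with a linear mixed model for repeated measures (SPSS MIXED):

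- Use every available baseline, 3-month and 6-month value, including observed visits from patients who stop or withdraw.
- Fit group, visit and group-by-visit terms with unstructured within-patient covariance.
- Make the randomised Lumega-Z versus AREDS2 contrast in 6-month change the main comparison. Include the untreated normal group only as a non-randomised reference.
- If both eyes are analysed, account for the correlation between eyes within a patient.
- Write this in place of the missing-data sentence, and fix it before the data are opened.
- Add one sensitivity analysis for dropout that depends on unobserved values, for example shifting the unobserved 6-month values over a stated range.

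The cost is SAP wording. No visits, patients or new software are needed. The downside is that the model assumes missingness depends only on observed data, which the sensitivity analysis is there to probe.

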27 DEC 2017

Controlled Study of the Effect of a Medical Food
Containing All Three Macular Carotenoids and Essential Cofactors
Compared to AREDS2 on Early Macular Degeneration

PURPOSE:

This 6-month randomized control study is undertaken to compare the effect of treatment with LumegaZ, a medical food containing lutein, zeaxanthin, and meso-zeaxanthin, as well as essential cofactors, other antioxidants, and mitochondrial support, with the effect of treatment with AREDS2. Patients with early macular degeneration, defined as photographically visible drusen with or without abnormal dark adaptation on the AdaptDx will be randomized 2:1 and both groups will be compared to untreated patients with normal dark adaptation.

BACKGROUND:

Macular degeneration is the most common cause of blindness in people over the age of 60. The incidence of macular degeneration at all stages is 1 in 8 and is more common than diabetes and glaucoma at the same age.

The dietary carotenoids lutein and zeaxanthin (derived primarily from leafy green vegetables and other colored fruits and vegetables) as well as meso-zeaxanthin, a metabolite of lutein, are stored in the macula in all healthy retinas. This area serves central vision, and is the specific area that is affected by macular degeneration. The accumulation of these pigments results in a yellowish coloration of the retina, the concentration of which is called macular pigment density. A large multicenter trial called AREDS 2 (2013) showed that supplementing lutein and zeaxanthin reduced progression of moderate to advanced AMD by 25%. The CREST (2014) and MOST (2015) studies showed that supplementation of all 3 macular pigments resulted in normalization of the macular pigment profile and improvement in contrast sensitivity in early AMD. All 3 macular carotenoids are recognized by the FDA as 'generally regarded as safe (GRAS) for supplementation in foods.

Macular degeneration can be understood as a disease of excessive oxidation of the retinal tissue with genetic, age, dietary and light exposure components leading to accumulation of oxidized cholesterol and polyunsaturated fatty acids both on Bruch's membrane and between Bruch's membrane and the retinal pigment epithelium in a condition analogous to plaque

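### Does leaving the unit of analysis (patient or eye) unnamed put the LumegaZ versus AREDS2 comparison at risk?

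*Combined protocol and SAP*

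**What the plan says.** The statistical analysis text (no heading, end of the combined document) says that strategies may include a "mixed-design Analysis Of Variance (ANOVA) to examine the following outcome measures across the three time-points of data collection". The outcomes listed after this include all three primary endpoints of STUDY REQUIREMENTS: macular pigment optical density, contrast sensitivity and vision. As a further option, "each group-measurement may be separated and analyzed by eye; to evaluate inter-eye differences from each treatment". The text closes: "Results of the statistical analysis will be analyzed as group averages of each outcome measurement". On the data handed to the analysts it says: "The data provided will only contain patient ID, age, and sex".

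Elsewhere the plan speaks of patients. Under PURPOSE, patients with visible drusen "with or without abnormal dark adaptation on the AdaptDx will be randomized 2:1". Under STUDY, those confirmed as eligible "will receive treatment by ingesting a commercially available medical food, containing all 3 macular pigment as well as essential cofactors and other antioxidants, or AREDS2". STUDY REQUIREMENTS says "The study population consists of 90 male and female patients in a routine clinical practice age 60 and over" and "The patient will be studied for improvements in ocular function".

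The available text names no study eye, no rule for combining two eyes, and no row unit for the ANOVA.

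**The concern.** The optional comparison between eyes is possible only if both eyes are measured for at least some outcomes, so an analyst may hold two values per patient per visit. Treatment is systemic and assigned to the person, so the two eyes of a patient always share an arm and their changes are likely to be correlated. If each eye became its own row, the test would treat up to 180 records as independent when at most 90 people were randomised. With positive correlation the standard error is then too small, and LumegaZ could appear to differ from AREDS2 by chance more often than 5% of the time. All three primary endpoints may pass through this ANOVA. With the unit unwritten, one could also worry that it would be chosen after seeing which version gives the smaller p-value.

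**Working it through.** **No stated figure to reproduce.** The documents give no alpha, power, effect size or standard deviation behind the 90 patients. The check therefore asks what each way of handling eyes would do to a nominal two-sided 5% test.

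**Inputs from the documents:** 90 patients; 2:1 allocation, so 90 × 2/3 = 60 versus 30 if all 90 are randomised; three visits.

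**Assumptions:** two complete eyes per patient; inter-eye correlation of change r from 0 to 0.9; group-by-time as the test of interest; LumegaZ and AREDS2 as the only two groups.

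**Degrees of freedom.** Patient rows: 2 and 2 × (90 − 2) = 176. Eye rows: 2 and 2 × (180 − 2) = 356.

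**Formula.** Stacking two eyes inflates the variance of a group mean by 1 + r relative to what the eye-level residual assumes. The 5% point of chi-squared on 2 df is 5.991, so the true rejection rate is about exp(−5.991 / (2(1 + r))). At r = 0.5 this is exp(−5.991/3) = 0.136, and the 180 eyes carry the information of 180/1.5 = 120 independent ones.

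**Results, no true difference, 60 versus 30** (20,000 simulated trials per row):

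| r | Eyes as records, formula | Eyes as records, simulated | Two-eye mean, simulated | Eyes significant, mean not |
|---|---|---|---|---|
| 0.3 | 0.0998 | 0.0973 | 0.0497 | 0.0476 |
| 0.5 | 0.1357 | 0.1343 | 0.0498 | 0.0845 |
| 0.7 | 0.1717 | 0.1711 | 0.0491 | 0.1220 |
| 0.9 | 0.2067 | 0.2064 | 0.0477 | 0.1587 |

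At r = 0 the eye version rejects 0.0505, so there is no inflation. A split of 40 versus 20 gives 0.0960 to 0.2093 for eyes and 0.0467 to 0.0509 for patient means. For a single test of 6-month change, 2(1 − Φ(1.96/√(1 + r))) gives 0.0856, 0.1095, 0.1328 and 0.1551 at the four values of r.

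**One eye per patient.** A separate run (8,000 trials per setting) rejects 0.047 at r = 0.5 and 0.051 at r = 0.8. The same holds for a right-eye or a left-eye analysis taken alone, since each has one row per patient.

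**Which of these does the plan point to?** A mixed-design ANOVA has a between-subject factor (group) and a within-subject factor (time). The only subject the plan randomises, counts and gives an ID to is the patient. The eye sentence is introduced as an addition and speaks of separating the data by eye, which yields one row per patient in each part. No sentence asks for eyes to be pooled as independent records. Every ordinary way of following the text therefore lands in a column that holds 5%.

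**The case for a change.** The strongest opposing case is that silence permits the bad choice as well as the good one. The sentence on group averages does not say averages of what, and calling the patient the object of study does not define a data row. One sentence would close the question at almost no cost, and the patient ID already links the eyes. All of that is true, and the arithmetic above is not in dispute.

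Two further points stand. First, the sound options are not interchangeable in power: with an assumed 6-month effect of 0.5 within-eye SD (half of it at 3 months) and r = 0.5, the two-eye mean rejects in 35% of trials and one eye in 27%. Second, an analyst who models both eyes with only a patient random intercept on three-visit data does not restore the level; under the assumed patient-by-visit variance, rejection was 8.1%, 12.1%, 17.0% and 21.6% at the four values of r. Such a model needs to allow for patient-by-visit correlation.

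Other parts of the case weaken on inspection. The shift towards significance is not strictly one-way. If 30% of patients contribute one eye, eye-level rejection falls to 9.3–17.7%, and the patient mean is significant when the eye version is not in 0.02–0.5% of trials. With 50% the figures are 7.5–14.7% and 0.2–0.75%. Against a one-eye analysis the reverse case reaches 2% at r = 0.3. More than two ways of handling eyes are open, and most are sound. The ANOVA itself is only something the plan may use, its decisive term is not named, and it might include the untreated normal group. The inflation thus belongs to a procedure the plan does not state.

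**Conclusion.** The concern does not call for a change. The omission is real: the available analysis text names no unit. The harm, however, arises only if an analyst stacks both eyes as independent records, which the plan never directs and which runs against its patient-level randomisation, count and identifier. If that were done, with two complete eyes in each of 60 versus 30 patients and r between 0.3 and 0.9, a nominal 5% group-by-time test would reject about 10% to 21% of the time. With one value per patient the rate is about 5%. With both eyes complete, the estimated group difference is the same for stacked eyes and two-eye means; only the standard error, interval and p-value move. The correlation, the number of eyes measured and the choice of test are all assumptions, because the documents give none of them. Naming the patient as the unit would record what a competent analyst would do anyway; it would not correct a rule the plan contains.
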